### **6.2 Inclusion Criteria**

1. histologically confirmed adenocarcinoma of the prostate, clinically localized, low or low-intermediate risk disease (T1C/T2a, Gleason≤7 (3+4), PSA < 20);
2. primary treatment is AS with planned annual surveillance biopsies;
3. BMI≥25 kg/m^2; and
4. physically able to undertake a diet and exercise program

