## 7.5 Clinical Assessments

Study visits will occur at baseline, 3, 6 and 12 months. During study visits, participants will undergo anthropometrics, fasting blood studies and/or complete physical activity, food diaries and HRQOL questionnaires. Assessments at 6 months will be used to evaluate the effectiveness of the intervention, and at 12 months will evaluate maintenance of the intervention.

Anthropometric Measurements. Height will be measured at baseline only, and weight, waist (1" above umbilicus), hip circumferences will be measured at baseline, 3, 6 and 12 months. Dual x-ray absorptiometry (DXA) using a GE Lunar iDXA will be obtained to measure overall percent body fat, lean mass and total bone density at baseline and 12 months.

Twelve-hour fasting blood. Fasting blood samples will be collected at baseline, and at 3, 6, and 12 months. Vacutainers will be labeled with participants' study ID and date, processed within 1 hour of collection and stored at -70°C.

Prostate Tissue. As part of the consent to participate in this study, participants are asked to give permission to investigators to allow a) the collection of two extra prostate biopsy cores during their standard-of-care biopsy (UW and VA participants only), and b) access to pathology tissue from a pre-study biopsy (that was already collected as part of routine medical care for diagnostic purposes) to be used for this study (UW and VA participants only). For VA patients, separate consent allowing the collection of extra biopsy cores during a standard-of-care biopsy, and allowing access to biopsy tissue after used for diagnostic purposes will be obtained at the VAPSHCS by VA study staff on the day of their scheduled biopsy. For participants who are not patients at UW or the VA, since the collection of extra biopsy cores is not possible, they will be asked to sign a separate "Release of Information" allowing access to prostate biopsy tissue collected as part of their routine care. Tissue blocks, fixed in formalin and embedded in paraffin (standard for AS biopsies), will be sent to [name] laboratory. Participants will be enrolled on study so that the intervention calendar coincides with routine clinical care; no extra biopsies will take place outside of the routine clinical care. Tissue blocks will be cut and sections mounted on charged slides.

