**Tissue Biomarkers.** pIR/IR, pIGF-IR/IGF-IR and pAKT/AKT protein expression will be assessed by IHC. Sections will be rehydrated and incubated with 3% H2O2, blocked with avidin/biotin blocking solution (Vector Laboratories Inc.) and then 5% goat serum. The sections will be incubated with either rabbit anti-IGF-1R $\alpha$  (1:100; Santa Cruz Biotechnology), rabbit anti-phospho-IGF-1R (1:50; Abcam), mouse anti-insulin receptor (1:100; Santa Cruz Biotechnology), rabbit anti-phospho-insulin receptor (1:50; Abcam), rabbit anti-AKT, rabbit anti-phospho-AKT (1:50; Cell Signaling) or rabbit or mouse control IgG at the same concentration, washed and incubated with biotinylated secondary antibody (1:100; Santa Cruz Biotechnology), developed using the Vectastain ABC kit (Vector Laboratories Inc.) and stable DAB (Vector Laboratories), counterstained with hematoxylin, dehydrated, and mounted with Permount (Fisher). All staining will be performed in [name] laboratory. A research pathologist will score the staining and be blinded to intervention arm. Blind duplicates (5%) will be included. IHC staining intensity for each tissue section will be determined as follows: 0=no staining, 1=faint/present staining, 2=strong/intense staining. The percentage of staining cells is then estimated and a composite score calculated by multiplying mean intensity score and percent cells stained positively, and then dividing by number of cores taken.

**Pathologic Features.** Pathologic findings will be recorded from the baseline and post-intervention biopsies, including Gleason grade, number of cores taken (12 core biopsy is standard); number of cores with cancer, and the percentage of each core involved with cancer. Adverse pathology on surveillance biopsy will be indicated by any of the following: a  $\geq 1$  pt increase in Gleason grade, an increase to  $> 50\%$  of any one core involved with cancer, and/or an increase in the number of cores involved with cancer.

**Intervention Sustainability.** Participants will return to the clinic 6 months after the active intervention ends to assess whether they have continued to follow the lifestyle intervention on a long term basis. Additional measures of blood glucose, weight and quality of life will be assessed.

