**Secondary Aim 1.** We will test whether the change in HRQOL, namely urinary and sexual QOL and bother, relative to baseline, differs between the intervention and control arms. Intervention effects will be evaluated using a two-sided t-test, and models will be adjusted for age, SES, marital status, and baseline BMI. The minimally important difference for the HRQOL instruments will be a mean difference of at least 5 points.

**Secondary Aim 2.** We will use a two-sample test of proportions to determine whether the proportion of participants with adverse pathology (Gleason upgrading, increase in number of positive cores, cores>50% positive) on follow-up surveillance biopsy differs between intervention and control arms.

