Insulin receptor	30 (34)	13.9	29.2%
IGF-1 receptor	112 (80)	32.7	46.3%
AKT	128 (83)	33.9	26.5%

shown the following results: a low-fat/low-carbohydrate diet can reduce expression of IR; low-fat, or caloric restriction diets can reduce expression of IGF-1R by 40%; and low-fat and/or low-carbohydrate and no carbohydrate diets reduce expression of AKT by up to 60%. Based on these observations, we have very good power to detect changes in IR, IGF-1R and AKT expression on epithelial cells from PCa biopsies.

Table 5 indicates the minimal detectable differences in change, and the power to detect a 5-point change between arms for each QOL tool. For most HRQOL assessments, we have good power to detect the designated minimally important differences (5-points) in QOL scores. Analyses of the association between the intervention and adverse pathology are exploratory in nature; thus, power is limited for this endpoint. Based on our clinical experience, approximately 25% of patients have 'adverse pathology' on their follow-up biopsy. Given the sample size in this study, we will be able to detect a 15% difference between intervention and control arms in the proportion of participants with adverse pathology on follow-up biopsy.

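### Adverse pathology counts any rise in positive cores and is tested only as yes/no, so re-sampling an unchanged tumour can dilute an effect on tumour extent; a baseline-adjusted core-count analysis should be added beside it

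*Combined protocol and SAP*

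**What the plan says.** Section 7.6, Pathologic Features, defines adverse pathology as any one of three findings: a Gleason rise of at least one point, a rise to more than half of any one core, "and/or an increase in the number of cores involved with cancer". It sets no minimum rise in cores and does not relate the rise to the number of cores sampled.

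The same section records, at both biopsies, the "number of cores taken (12 core biopsy is standard" figure in its own wording) and the "number of cores with cancer, and the percentage of each core involved with cancer".

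Section 11, Secondary Aim 2, gives one analysis: "We will use a two-sample test of proportions to determine whether the proportion of participants with adverse pathology" differs between arms. The synopsis and Section 5.2 say the same. No between-arm comparison of core counts is planned.

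Section 11.1 states that "approximately 25% of patients have 'adverse pathology' on their follow-up biopsy" and that "we will be able to detect a 15% difference between intervention and control arms". It also calls this endpoint exploratory, with limited power. Section 6.2 admits "clinically localized, low or low-intermediate risk disease (T1C/T2a, Gleason≤7 (3+4), PSA < 20") and sets no limit on positive cores.

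**The concern.** Each man's threshold is his own single baseline count plus one. A needle biopsy samples a small part of the gland, so a second biopsy of the same tumour can give a higher count by chance. Such rises occur at the same rate in both arms when sampling is the same. They are events that an intervention which only stops growth cannot prevent, so they pull the difference in proportions towards zero. The yes/no coding also ignores the size of the change and the baseline count, both of which are recorded.

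At stake is how a null result is read. This is the plan's only between-arm comparison of biopsy pathology, and slowing progression is the trial's rationale. A diluted null could be taken as evidence of no effect on tumour extent.

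**Working it through.** **1. The plan's own figure.** Inputs from Section 11.1: 25% adverse, a 15-point difference, 100 per arm, 5% drop-out (95 per arm). The two-sided 5% level is stated there for the primary aims and assumed to carry over.

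Power = Φ{[|p1 − p2| − 1.96·√(2p̄(1 − p̄)/n)] / √[(p1(1 − p1) + p2(1 − p2))/n]}

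For 25% v 10% at n = 100: (0.15 − 1.96 × 0.0537)/0.0527 = 0.85, so power is 80.2% (78.1% at n = 95). The stated figure reproduces, for a reduction.

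**2. Chance of a rise with no change in the tumour.** Assumptions, none from the documents: 12 cores at both biopsies, independent cores with the same positivity p, and at least one positive core at baseline. Let P0 be the probability of no positive core and T the probability that the two counts tie. Then

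P(rise | baseline ≥ 1) = [(1 − T)/2 − P0(1 − P0)] / (1 − P0)

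The mean below is 12p, before restricting to men with a positive core.

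| Mean of 12 | P0 | T | Chance of a rise |
|---|---|---|---|
| 0.5 | 0.600 | 0.464 | 7.0% |
| 1 | 0.352 | 0.312 | 17.9% |
| 2 | 0.112 | 0.220 | 32.7% |
| 3 | 0.032 | 0.188 | 38.8% |

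Example, mean 1: (0.344 − 0.228)/0.648 = 0.179.

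A second model fixes the tumour in a few sectors, each hit with a given probability. One sector gives 0%, since a positive baseline is already the maximum. Two sectors give 7% (hit probability 0.3), 17% (0.5), 23% (0.7) and 15% (0.9). Four sectors at 0.7 give 34%.

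**3. Effect on the 15-point claim.** Suppose the 25% uses the Section 7.6 definition, and the intervention stops growth without shrinking tumours. The intervention arm then cannot fall below the chance rate. A 15-point difference needs a chance rate of 10% or less (25 − 10 = 15). At 17%, preventing all true progression leaves 25 − 17 = 8 points, with power 28% at 100 per arm and 27% at 95.

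**4. Yes/no coding against core counts.** Simulation with 95 per arm, mean 2 of 12, between-man beta variation (concentration 10 and 20) and at least one positive core at baseline. The regression is linear: follow-up positive fraction on arm and baseline fraction.

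| Assumed effect | Yes/no test | Regression |
|---|---|---|
| None | about 5% | about 5% |
| Core positivity 25% higher in controls, nothing else | 39–41% (any rise) | 61–63% |
| Upgrading 20% v 8%, core positivity 10% higher in controls | about 39% (upgrading or any rise) | 15–16% |
| Upgrading 25% v 10% only | about 30% (upgrading or any rise) | about 5% |

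In the second row the any-rise rates are about 42–43% v 30–31%, above the plan's 25%. At a mean of 1 the control rate is 18–24%, which fits within 25%. There, a 30% lower core positivity in the intervention arm gives 36–50% power for any rise against 62–77% for the baseline-adjusted count analysis (95 per arm). Requiring a rise of at least two cores, in the second-row scenario, gives 37–39% and so recovers nothing.

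**The case against.** The strongest reply is that every chance rate above is assumed. A reader might infer that re-sampling makes some 17–39% of men adverse, or that the composite mostly measures re-sampling. The documents do not support either. They give no baseline core distribution and no repeatability, the population is low or low-intermediate risk, and sparse disease takes the rate to 7% or to zero. If the 25% in Section 11.1 uses the Section 7.6 definition, a chance rate above 25% is impossible. That figure rests on clinical experience and its definition is not given, so it neither confirms nor excludes a high rate. This part of the reply stands.

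A reader might also infer that the composite should be replaced or demoted. The last two rows of the second table argue against that: where the intervention acts on Gleason grade, the composite does better and the core regression sees little or nothing. Section 1.5 names upgrading, along with a greater amount of cancer, as evidence of progression, and the composite follows that description. This stands too.

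Nor is there a false-positive problem, because chance rises are equal between arms. A confirmatory biopsy is not available, as Section 4.1 rules out biopsies solely for the study. Finally, Section 11.1 already labels the endpoint exploratory with limited power. That limits how much the point matters, but it does not explain leaving recorded counts out of the arm comparison.

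**Conclusion.** The point holds in a limited form. Counting any rise in cores and testing only a proportion lets re-sampling dilute an effect on tumour extent, with type I error intact. The chance rate lies between near 0% and about 39% under the assumptions in step 2. It could be a substantial part, possibly most, of the assumed 25%, but the documents cannot fix it.

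A baseline-adjusted count analysis gains about 20 points of power for effects on core counts in the main scenario (61–63% against 39–41%), and none for effects on upgrading. The power figures for any rise cover the core-count component alone, not the full composite. This is an inexpensive improvement to an exploratory secondary analysis; the primary aims are unaffected.

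**What to change.** Keep the composite and its test of proportions as planned. In Section 11, Secondary Aim 2:

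- Add a pre-specified supplementary comparison of tumour extent: regress positive cores out of cores taken at follow-up on arm and baseline positive fraction (a linear model on the fraction, or quasi-binomial).
- Report Gleason upgrading, a new core above 50% and a rise in core count separately by arm.
- State which cores enter the numerator and denominator, because Section 7.5 provides for "the collection of two extra prostate biopsy cores during their standard-of-care biopsy (UW and VA participants only") and does not say whether they count.

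Do not write a chance rate such as 17–39% into Section 11.1 as an expected value; the documents offer no source for it.

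The cost is a few lines of text and one regression on data already recorded, with no new patients, biopsies or readings. The downside is one more exploratory analysis, with an effect measure (difference in fraction of positive cores) that is less familiar to clinicians than a rate.

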### **Quality of Life Outcomes.**

**Memorial Anxiety Scale for Prostate Cancer (MAX-PC).** The MAX-PC will measure anxiety related to PCa.

MAX-PC contains subscales that assess general PCa anxiety, anxiety regarding PSA level, and fear of PCa recurrence.

EQ-5D-5L. The EQ-5D-5L is a generic QOL instrument. It is extensively validated and includes domains of mobility, self-care, activity level, pain/discomfort, and anxiety/depression. EQ-5D-5L responses can be used to calculate health state utilities for health economic analyses.

Expanded Prostate Cancer Index (EPIC) Short Form. The EPIC will measures urinary and sexual function and bother. EPIC survey results are transformed into summary scores scaled from 0-100, with a higher score indicating better QOL.

## 8 RISK / BENEFIT ASSESSMENT

### Potential Risks

1. Participants may experience a little discomfort or have a temporary bruise from having blood drawn. Occasionally a participant may feel lightheaded or feel faint when having blood drawn.
2. There is a small risk of medical problems occurring during or after exercise testing.
3. The major risks of participating in this monitored program include fatigue, muscle soreness, and possible joint or skeletal injury or other unspecified medical events.
4. Some participants may feel that coming to clinic visits (including the nutrition and physical activity curriculum training sessions) may be inconvenient and/or burdensome.
5. Some participants may feel that the quality of life questionnaires about sexual and urinary function are embarrassing.
6. Other potential risks are associated with the collection of personally identifiable and health information from the subjects, and the potential for (a) psychological harm if the subject learns they have a disease or medical condition they were previously unaware of; and (b) a financial and/or employment risk, as a breach of confidential information could make it harder for the subject to find health insurance, life insurance, or employment.

### 8.1 Protection Against Risks

In the event that this research activity results in an injury, medical treatment will be available, including first aid, emergency treatment and follow up care, as needed. All procedures involving blood collection, DXA, exercise testing and anthropometry will be done at the FHCRC Prevention Center Clinic. Trained staff will be available to assist should a medical emergency occur. An MD licensed in Washington State is the Prevention Center Director. Participants will be informed in the written consent form that payment for any such treatment must be provided by the individual and/or the individual's insurance company.

1. Blood draws are associated with certain physical risks such as bruising, fainting, or phlebitis. We will minimize these risks by making sure that all blood draws will be conducted by well-trained phlebotomists at the FHCRC Prevention Center. Subjects will be asked before the blood draw if they have experienced problems with blood draws in the past, and will be offered an opportunity to lie down during the procedure if they wish. In our experience, blood draws performed in this manner are well tolerated, and any side effects are minimal. Participants should be able to tolerate the loss of 10-20 cc of blood without negative health consequences.
2. We will screen participants so that only participants with no known heart conditions will be tested. Persons with a serious heart condition will not be eligible for this study. Participants may feel tired during or after the exercise test. Recovery generally occurs within 30 minutes. Participants will be continuously monitored and the test will be stopped at any time the participant asks (an emergency stop mechanism is available for subjects to use). A technician with Advanced Cardiac Life Support (ACLS) certification will be present at all times. In persons with an underlying heart condition, there is a slight (less than 1 chance in 1,000) risk of having a sudden heart attack and an even slighter (less than 2 chances in 10,000) risk of sudden death.
3. The risks associated with the exercise intervention will be reduced by proper warm-up/cool-down periods, instruction from a trained exercise specialist at a slow-paced progression which will be determined by the participants' current fitness level and careful monitoring by an exercise specialist. The exercise specialists will teach participants techniques to minimize joint or muscle injury. The risk of medical adverse events is greatly reduced by having all participants complete and pass an exercise test prior to entering the program.

4. We will make every effort to schedule participants to come to the FHCRC at times that are convenient for them. This includes all sessions with the study dietitian and exercise specialist.
5. Participants may choose to not answer any questions that make them feel uncomfortable or embarrassed.
6. To minimize the risk of breach of confidentiality, we will make sure that all health information and records are labeled with a study identification number and initials. Personally identifiable information will be kept physically separate from any health information, and only one computer file will link the study identification number to the personally identifiable information such as name, address, telephone number, or e-mail address. Only the PI, study coordinator and study staff will have access to this password-protected file.
7. In the extremely rare and unexpected event of an emergency while subjects are attending to the Fred Hutch Prevention Center, a staff member and study staff will be on hand at all times throughout the visit to call for help as needed, and a physician will be on call. For complications arising among subjects that have left clinical facilities, subjects will be provided with the telephone numbers of the PI and the study coordinator, and will be encouraged to call with any problems at any time. Participants will be encouraged to call 911 in case a life-threatening emergency occurs; such an event is unlikely, and it would be extremely unlikely to be related to the study procedures.

## 8.2 Potential Benefits

Participants will be paid \$100 upon completion of the study to help compensate for time and travel.

Participants will receive small study-branded gifts during the study in appreciation of their participation in the study. Below is the plan for distribution of these items:

	Intervention	Control
PALS squeeze apple and gel pack	Clinic visit 1	Clinic visit 4
PALS hat	Clinic visit 3	Clinic visit 4

The data generated from this proposed research study will provide essential information for the scientific community involved in making recommendations for optimal diet and physical activity regimens for men with prostate cancer undergoing active surveillance. This is an important area of research because if lifestyle factors can be shown to improve measures of glucose control, energy balance and subsequent health of prostate cancer patients, then it will have far reaching implications for the thousands of men undergoing active surveillance – hopefully demonstrating that lifestyle changes can prevent more invasive and life-altering procedures (i.e. radical prostatectomy). Thus, with minimal risk to study participants, we will generate data that will be beneficial to men with localized prostate cancer.

Overall, using this proposed study design, we have attempted to minimize any potential risks to study participants, whilst maximizing the amount of important scientific data that can be generated and ultimately shared with the scientific community and the general public.

## 9 DISCONTINUATION AND REPLACEMENT OF SUBJECTS

### 9.1 Early Discontinuation of Study Treatment

A subject may be discontinued from study treatment at any time if the subject, the investigator, or the Investigator feels that it is not in the subject's best interest to continue. The following is a list of possible reasons for early discontinuation of study treatment:

- Participant decision
- Adverse event
- Protocol violation
- Death

If a subject is discontinued from treatment due to a related adverse event, the subject will be followed and treated by the Investigator until the abnormal parameter or symptom has resolved or stabilized.

